7.3. Center Pooling

Due to the feasibility nature of this study and reduced sample size, statistical comparisons of sites' performance will not be performed.

7.4. Handling of Missing Data and Dropouts

Missing data will not be imputed. In order to be included in the primary analysis, an ADHF event must have LINQ™ data downloads for at least the most recent 30 days prior to the event. If device data are missing, the event will not be included in the primary analysis.

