8.12 Monthly CareLink Transmissions

Subjects are required to perform a manual device transmission monthly from the time they are enrolled in the study until their Study Exit visit. [REDACTED]

[REDACTED] The subject will utilize the MyCareLink® Home Monitor to manually transmit the data. The subject will receive instructions on how to perform the manual transmission. Refer to Appendix G.

As described above, a Monthly Device Transmission eCRF will be required to be completed to ensure the subject manually transmitted. A study deviation will be required for any missed monthly manual Carelink transmissions, unless a device interrogation file for an interrogation occurring within the required timeframe is provided to Medtronic.

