14.4 Missing Data

Missing data will not be imputed. In order to be included in the primary analysis, an ADHF event must have complete LINQ™ data downloads prior to the event. If device data is missing, the event will not be included in the primary analysis.

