7.9.4. Analysis Methods

Physiologic data (including heart rate, bioimpedance, activity, blood pressure and weight), as well as blood samples (including serum BUN, creatinine, NT-proBNP, hemoglobin, hematocrit, troponin, eGFR and electrolytes), will be collected from subjects with acute decompensated heart failure. [REDACTED]

This document is electronically controlled. Printed copies are considered uncontrolled.

Confidential

The following table lists out the RAMware features and frequency of measurements.

[REDACTED]	[REDACTED]	[REDACTED]
[REDACTED]	[REDACTED]	[REDACTED]
[REDACTED]	[REDACTED]	[REDACTED]
	[REDACTED]	[REDACTED]
	[REDACTED]	[REDACTED]
[REDACTED]	[REDACTED]	[REDACTED]
	[REDACTED]	[REDACTED]
[REDACTED]	[REDACTED]	[REDACTED]

[figure not shown]
Data will be collected from enrollment up to 3 years post-insertion. If a subject exits the study prematurely, data captured prior to exit will be included in the analysis. All data collected will be included in the analysis. Descriptive statistics (e.g. means, standard deviations, proportions) will be used to summarize the physiological and derived data recorded. Analyses will be conducted to assess changes in the physiologic and LINQ™ derived data in association with HF events.

For each subject whose device contains the downloaded RAMware, the measurements in the table above will be averaged to produce one mean value for each feature for each day. Then for subjects who experience at least one ADHF event, the daily mean values will be averaged across subjects for each day leading up to the first event per subject and each day following that event for a minimum of 14 days on either side of admission. For example, if 40 subjects have at least one ADHF event, then for each of the 14 days prior to that event, the 40 subjects' mean values for that day will be averaged. The same will be done for the 14 days following ADHF admission. This will be done for each of the features above.

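### Dropping a whole ADHF event for missing 30-day device data does not fit the planned day-by-day averages, and it puts subjects with real events into the no-event reference curve

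*Combined protocol and SAP*

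**What the plan says.** - **Entry rule.** SAP 7.4 says that "an ADHF event must have LINQ™ data downloads for at least the most recent 30 days prior to the event". It continues: "If device data are missing, the event will not be included in the primary analysis". It also states: "Missing data will not be imputed".
- **Protocol counterpart.** Protocol 14.4 says that "an ADHF event must have complete LINQ™ data downloads prior to the event" and gives no window length.
- **Planned summary.** In SAP 7.9.4 the measurements are "averaged to produce one mean value for each feature for each day". These daily values are then averaged across subjects, separately for each day before the first event and "each day following that event for a minimum of 14 days on either side of admission". The worked example uses 14 days. The same section says that all collected data enter the analysis.
- **Reference curve.** The last paragraph of SAP 7.9.4, like SAP 7.1.3, assigns to the reference group any subject without an ADHF event used in the analysis. SAP 7.2 describes that group's purpose as showing measurements that do not precede an ADHF event.
- **Data route.** Protocol 8.12: "Subjects are required to perform a manual device transmission monthly". An interrogation file from the required timeframe can stand in for a missed transmission. After a death, protocol 11.5.1 asks for interrogation when possible.
- **Event target.** SAP 6 and 7.2 count the 40 events among those that already have the 30 days of data.

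**The concern.** A mean taken separately for each day does not need every event to be complete on every day. An event with days -14 to -1 intact but data missing somewhere in days -30 to -15 could supply every pre-event daily mean the SAP commits to. SAP 7.4 removes it altogether.

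Two things follow. First, the pre-event curve may describe an unrepresentative set of decompensations if data are more often missing around certain kinds of event. The plan has no table that would show this. Second, a subject whose only event is removed by the data rule has no event used in the analysis, so that subject's days, including those just before a real decompensation, are plotted as no-event reference data. This works against the purpose given in SAP 7.2.

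**Working it through.** **1. The plan's own figures.** SAP 6 takes 300 subjects and a 25% 12-month event proportion, with 16% as the lower case. The exact binomial P(X ≥ 40) is above 0.999 at 25%, as stated (>99%). At 16% it is 0.912, matching the protocol's >91%. The SAP's >88% matches P(X ≥ 41) = 0.883. Neither calculation allows for events lost to missing device data.

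**2. Loss of events (assumed model).** The documents give no missingness rate. Assume data arrive in 30-day blocks, each present independently with probability c, and that the event falls at random relative to block boundaries. A 30-day window lies within one block in 1 of 30 alignments and spans two in the other 29.

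- Kept under the 30-day rule: c/30 + 29c²/30.
- c = 0.95: 0.0317 + 0.8724 = 0.904, so 9.6% of events are lost.
- c = 0.90: 0.030 + 0.783 = 0.813, so 18.7% are lost.

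A 14-day window lies within one block in 17 of 30 alignments.

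- Intact 14-day run-up: 17c/30 + 13c²/30.
- c = 0.95: 0.5383 + 0.3911 = 0.929. c = 0.90: 0.510 + 0.351 = 0.861.
- Events with an intact 14-day run-up that are still dropped: 0.929 − 0.904 = 2.5% and 0.861 − 0.813 = 4.8% of all events.

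Averaging over whatever days exist loses 1 − c of event-days, that is 5% and 10%.

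**3. Effect on accrual.** Let f be the share of events kept. P(at least 40 usable) is the binomial tail with n = 300 and proportion p × f.

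| Loss | p = 25% | p = 16% | Events needed for 40 usable |
|---|---|---|---|
| 0% | >99.9% | 91.2% | 40 |
| 10% | >99.9% | 72.4% | 45 |
| 20% | 99.9% | 41.7% | 50 |

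These cover first events within 12 months only. Second events and follow-up to 3 years add to the count.

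**4. Reference group (illustration).** Take all 300 subjects as inserted, 25% with an event (75), and one event each. Excluding 9.6% or 18.7% moves 75 × 0.096 = 7.2 or 75 × 0.187 = 14.0 subjects into a reference group of 225. Their share is 7.2/232.2 = 3.1% or 14.0/239.0 = 5.9%.

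**5. What the model does not show.** Blocks are missed at random here, so the figures size the loss and not any bias. The documents give nothing from which the direction or size of a bias could be computed.

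**The case against.** - **The target already absorbs the loss.** SAP 6 and 7.2 count the 40 events after the data rule, so an excluded event prolongs accrual and does not by itself shrink the analysed set. This stands. A reader might infer from SAP 7.8, which lets follow-up end at 40 events without repeating the data condition, that fewer than 40 would be analysed. SAP 6 and 7.2 state the condition, so I do not rest the point on that sentence.
- **Missing may not mean a single day.** The rule speaks of downloads, and the term is undefined. A reader might infer that one lost day removes an event, so that 1% independent daily loss keeps only 0.99^30 = 74% of events. That is one reading of the wording, and independent daily loss has no basis in the documents.
- **Thirty days may have a purpose.** Fourteen days is a minimum, longer curves are allowed, and 30 days matches the post-implant criterion in SAP 7.9.2. The feature table in SAP 7.9.4 is redacted, so the run-up each feature needs cannot be judged. A complete set also keeps the same events behind every pre-event day. This is a good reason to keep the 30-day set alongside an available-day average.
- **Selective loss is not shown.** Data can be recovered by a later interrogation, including after death, and text following the monthly requirement in protocol 8.12 is redacted. It would go too far to say that the curve will describe only compliant survivors. What stands is that reliance on manual transmission, and on interrogation after death only when possible, makes selective loss possible, and the plan offers no way to see it.
- **Extra analyses are allowed.** SAP 7.9.2 permits analyses of all qualifying events. In context that lifts the two-event cap; it does not say that events lacking device data return.
- **The study is descriptive and has no hypotheses.** True, and it limits the stakes. The curves are nevertheless its main product.

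**Conclusion.** The mismatch is real: exclusion is by whole event, while the summary is by day. Under the assumed block model at 90–95% completeness, the rule loses about 10–19% of events, against 5–10% of event-days with available-day averaging. About 2.5–5% of all events would be dropped despite an intact 14-day run-up. The number analysed need not fall, and accrual becomes tight only if the event proportion is near 16%.

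The point therefore rests on representativeness, where selective loss is possible but undocumented, and on the reference group, where the misplacement follows from the SAP's own wording. Its share is modest in the illustration (3–6%). This is a worthwhile low-cost improvement; it does not invalidate the design.

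**What to change.** 1. In SAP 7.4, state what counts as missing: a day, a feature or a download.
2. Keep the 30-day-complete set. Alongside it, present the day-by-day averages over all CEC-confirmed qualifying events that have a value on that day, with N printed for each day.
3. Tabulate CEC-confirmed events excluded for missing device data, by setting and by fatal or not.
4. In SAP 7.1.3 and 7.9.4, keep subjects with an excluded event out of the reference curve.
5. Reconcile SAP 7.4, the all-data statement in SAP 7.9.4, and protocol 14.4.

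The cost is SAP wording with matching protocol text, one extra run and one table; no new data are collected. The small downside is that the set of events varies by day in the available-day average, so an apparent trend could partly reflect changing composition. The 30-day-complete set is the check on that.

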7.5. Adjustments for Multiple Comparisons

No adjustment for multiple comparisons will be made. This is a single arm study.

This document is electronically controlled. Printed copies are considered uncontrolled.

Confidential

7.6. Demographic and Other Baseline Characteristics

Descriptive statistics will be used to summarize baseline and demographic characteristics. For categorical data such as gender and New York Heart Association classification, counts and percentages will be employed, while for continuous variables such as age, means, standard deviation, quartiles, minimum, and maximum will be provided. These statistics will be provided both for all enrolled subjects and for the subset of subjects who receive a LINQ device.

7.7. Treatment Characteristics

Descriptive statistics will be used to summarize all procedure information collected, including

- Time from procedure check-in to subject discharge
- Pre-procedure preparation time
- Procedure time (time subject enters the room to time subject leaves procedure room)
- Insertion time (time from first incision to skin closure)
- Pre-procedure preparation location
- Procedure location
- Location of inserted device (e.g. parallel to sternum over 4th intercostal space)
- Whether device was sutured
- Closure method used (e.g. staple(s), suture(s))
- Local anesthesia used
- Antibiotic agent(s) administered pre-procedure and post-procedure
- Location of subject education on their Reveal LINQ system, and total education time

Additionally, the percentage of subjects on CV medications will be assessed as of each follow-up visit. This will be done separately for relevant classes such as beta blockers, diuretics, and ACE-Inhibitors/ARBs.

7.8. Interim Analyses

No interim analyses are planned for this study. Since there is no interim analysis planned, there are no criteria for early termination based on statistical evidence. Once the requisite number of ADHF events have been obtained (a minimum of 40 occurring \geq 30 days post-implant among subjects with the RAMware downloaded to the subject's LINQ device, with no more than two ADHF events per subject), follow-up in the study may be terminated and all subjects exited.

This document is electronically controlled. Printed copies are considered uncontrolled.

Confidential

7.9. Evaluation of Objectives

The primary objective is to characterize Reveal LINQ™ derived data from patients with heart failure by assessing the relationship between changes in LINQ™ derived data and other physiologic parameters with subsequent ADHF events.

7.9.1. Hypothesis

Due to the feasibility nature of this trial, there are no hypotheses for this objective.

7.9.2. Performance Requirements

Performance requirements are not pre-specified for this objective. The ADHF events as adjudicated by the CEC that will be used in the primary analysis are those that are ≥ 30 days following implant in order to ensure sufficient LINQ™ derived data prior to the event onset are available. A second ADHF event within a subject may be used if the second ADHF event is > 90 days following the first event. In the event a subject has > 2 qualifying ADHF events, only the first two will be used in the primary analysis. Additional analyses including all qualifying ADHF events may be conducted.

A heart failure event is defined as any cardiovascular-related (including hypervolemia) Health Care Utilizations (HCUs) for any one of the following events.

- Admission with primary diagnosis of HF
- Intravenous HF therapy (e.g. IV diuretics/vasodilators) or ultrafiltration at any one of the following settings:
 - Admission with secondary/tertiary diagnosis of HF
 - Emergency Department
 - Ambulance
 - Observation Unit
 - Urgent Care
 - HF/Cardiology Clinic

7.9.3. Rationale for Performance Criteria

This is a feasibility study, and so this objective is for the purpose of gathering data for [REDACTED]

[REDACTED] this data will be used later for potential hypothesis generation regarding the predictive nature of one or more of these data elements for ADHF outcomes.

7.9.4. Analysis Methods

Physiologic data (including heart rate, bioimpedance, activity, blood pressure and weight), as well as blood samples (including serum BUN, creatinine, NT-proBNP, hemoglobin, hematocrit, troponin, eGFR and electrolytes), will be collected from subjects with acute decompensated heart failure. [REDACTED]

This document is electronically controlled. Printed copies are considered uncontrolled.

Confidential

The following table lists out the RAMware features and frequency of measurements.

[REDACTED]	[REDACTED]	[REDACTED]
[REDACTED]	[REDACTED]	[REDACTED]
[REDACTED]	[REDACTED]	[REDACTED]
	[REDACTED]	[REDACTED]
	[REDACTED]	[REDACTED]
[REDACTED]	[REDACTED]	[REDACTED]
	[REDACTED]	[REDACTED]
[REDACTED]	[REDACTED]	[REDACTED]

[figure not shown]
Data will be collected from enrollment up to 3 years post-insertion. If a subject exits the study prematurely, data captured prior to exit will be included in the analysis. All data collected will be included in the analysis. Descriptive statistics (e.g. means, standard deviations, proportions) will be used to summarize the physiological and derived data recorded. Analyses will be conducted to assess changes in the physiologic and LINQ™ derived data in association with HF events.

For each subject whose device contains the downloaded RAMware, the measurements in the table above will be averaged to produce one mean value for each feature for each day. Then for subjects who experience at least one ADHF event, the daily mean values will be averaged across subjects for each day leading up to the first event per subject and each day following that event for a minimum of 14 days on either side of admission. For example, if 40 subjects have at least one ADHF event, then for each of the 14 days prior to that event, the 40 subjects' mean values for that day will be averaged. The same will be done for the 14 days following ADHF admission. This will be done for each of the features above.

For subjects who have multiple ADHF events, plots may be produced with time on the x-axis, and daily average value for a particular feature on the y-axis, with periods in which the ADHF events occurred noted as well. The graph may have the following format. Because the lack of required follow-up visits beyond 12 months may result in ADHF events going unreported, a summary of the plot of a single subject's readings over time should include a marker at 12 months to denote the point at which required follow-up visits ended for this subject.

This document is electronically controlled. Printed copies are considered uncontrolled.

Confidential

Subjects who do not experience an ADHF event included in the analysis will have their daily data averaged across these subjects for each day post-insertion and plotted as reference for comparison with the data summaries described above.

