14.2.2 Analysis Methods

Physiologic data (including heart rate, bioimpedance, activity, blood pressure and weight), as well as blood samples (including serum BUN, creatinine, NT-proBNP, hemoglobin, hematocrit, troponin, eGFR and electrolytes), will be collected from subjects with acute decompensated heart failure.

[REDACTED] Data will be collected from enrollment up to 3 years post-insertion. If a subject exits the study prematurely, data captured prior to exit will be included in the analysis. All data collected will be included in the analysis. Descriptive statistics (e.g. means, standard deviations, proportions) will be used to summarize the physiological and derived data recorded. Analyses will be conducted to assess changes in the physiologic and LINQ™ derived data in association with HF events.

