7.2. General Methodology

Data analysis will be performed by a Medtronic statistician or designee, and will be performed once at least 40 ADHF events (as adjudicated by the CEC) occurring at least 30 days post-Reveal LINQ implant have been obtained from subjects who received the downloaded RAMware and have data for the most recent 30 days prior to the event. No more than two events per subject will be included in the analysis, and those two events must be at least 90 days apart.

All analyses will be performed on an "As Treated" basis.

The cohort will include all enrolled subjects who received the downloaded investigational LINQ HF RAMware and experienced ADHF events at least 30 days post-implant. Subjects who do not experience ADHF events may also be included as a reference dataset for baseline readings of measurements (i.e. profile of measurements that do not precede ADHF events).

Any tests of treatment effects will be conducted at a two-sided alpha level of 0.05 unless otherwise stated.

Any change to the data analysis methods described in the protocol will require an amendment only if it changes a principal feature of the protocol. Any other change to the data analysis methods described in the protocol, and the justification for making the change, will be described in the clinical study report.

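### SAP 7.9.4 shows the mean change before ADHF events, but the visible text states no own-baseline window and no precision for that change

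*Combined protocol and SAP*

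**What the plan says.** The objective is about change: "assessing the relationship between changes in LINQ™ derived data and other physiologic parameters with subsequent ADHF events" (SAP 7.9). Protocol 14.2.2 and SAP 7.9.4 both promise that "Analyses will be conducted to assess changes in the physiologic and LINQ™ derived data in association with HF events".

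The visible text spells out one pre-event calculation. Each feature is reduced to one mean per subject per day, and "the daily mean values will be averaged across subjects for each day leading up to the first event per subject". The window is at least 14 days either side of admission. On summary measures, SAP 7.9.4 says "Descriptive statistics (e.g. means, standard deviations, proportions) will be used to summarize the physiological and derived data recorded".

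The comparison data come from other people. Subjects without events "may also be included as a reference dataset for baseline readings of measurements" (SAP 7.2). Those without an analysed event "will have their daily data averaged across these subjects for each day post-insertion and plotted as reference for comparison" (SAP 7.9.4). Single-subject plots are optional and are for subjects with several events.

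SAP 7.4 requires that "an ADHF event must have LINQ™ data downloads for at least the most recent 30 days prior to the event". It uses this to decide which events qualify and does not call the period a baseline. SAP 7.9.1 states that there is no hypothesis, and SAP 7.5 says "No adjustment for multiple comparisons will be made".

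**The concern.** An objective about change calls for a summary of change: from which reference period, by how much, and how well estimated. The planned curve answers the second question. The first and third are not answered in the visible text.

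The reference curve does not fill the gap. It is built from different subjects and runs by day since insertion, so it has no day that corresponds to a given day before an event.

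SAP 7.9.3 says the results will feed later hypothesis generation. Whoever uses them must judge which features moved by more than the noise in a few dozen subjects. The planned output would show the size of a shift without the means to judge that, although the data required for each included event would provide it.

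**Working it through.** **1. What the planned curve estimates.** If the same subjects contribute on every day, the difference between two daily means equals the mean of the within-subject differences. The 30-day rule in SAP 7.4 is meant to secure this before the event. An own baseline therefore leaves the point estimate unchanged. What is missing is the stated window and the precision.

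**2. Number of subjects.** SAP 6 says 300 subjects at a 25% event proportion give at least 40 subjects with an event with probability above 99%. The exact binomial tail is 0.9999998, so that figure reproduces. However, SAP 7.2 and 7.8 trigger analysis on 40 events with at most two per subject, so the first-event summary could rest on as few as 40/2 = 20 subjects.

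**3. Inputs not in the documents.** No SD or within-subject correlation is visible. Assume a daily SD of 1 and vary the correlation. Take baseline B = days -30 to -24 and headline range H = days -7 to -1, seven days each.

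**4. Formula.** Var(change) = r_BB + r_HH - 2 r_BH, where each r is the average correlation over the pairs of days (a day with itself counts as 1). The 95% half-width is t × √(Var/n), with t = 2.023 for n = 40 and 2.093 for n = 20.

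- Constant correlation ρ: r_BB = r_HH = (1 + 6ρ)/7 and r_BH = ρ, so Var = 2(1 - ρ)/7.
- Correlation a + (1 - a) × 0.9^lag: the 0.9^lag part averages 0.798 within a window and 0.093 between windows, so Var = 1.410 × (1 - a).

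| Assumed correlation | Var(change) | Half-width, n = 40 | Half-width, n = 20 |
|---|---|---|---|
| constant 0.3 | 0.200 | 0.14 | 0.21 |
| constant 0.5 | 0.143 | 0.12 | 0.18 |
| constant 0.7 | 0.086 | 0.09 | 0.14 |
| constant 0.9 | 0.029 | 0.05 | 0.08 |
| decaying, a = 0 | 1.410 | 0.38 | 0.56 |
| decaying, a = 0.3 | 0.987 | 0.32 | 0.47 |
| decaying, a = 0.5 | 0.705 | 0.27 | 0.39 |

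Every row has the same daily SDs and is compatible with the same daily means. At n = 40 they give the same interval for a single day's level, 2.023/√40 = 0.32 SD. Yet the half-width for the change ranges from 0.054 to 0.380, a factor of 7. The printed summaries cannot tell these cases apart.

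**5. How much drift each baseline hides.** Suppose a feature drifts linearly and reaches 1 at day -1. The headline range averages to its value at day -4.

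- Drift from day -21: headline mean 17/20 = 0.85. The baseline -30 to -24 contributes 0, so 85% of the day -1 change is shown. With baseline -30 to -15 the baseline mean is (21/20)/16 = 0.066, so 78% is shown.
- Drift from day -30: headline mean 26/29 = 0.897. The baseline -30 to -24 averages 3/29 = 0.103, so 79% is shown. With -30 to -15 it averages 7.5/29 = 0.259, so 64% is shown.

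The early, shorter window hides less. Its price in precision is small: with -30 to -15 and n = 40 the half-widths run from 0.05 to 0.33 SD, against 0.05 to 0.38.

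**The case against.** The strongest reply is that nothing is wrong. The curve shows the mean change, and the study is feasibility work with no hypothesis and no performance requirement. The list of descriptive statistics is given only as examples, so it does not exclude an interval. SAP 7.9.2 allows additional analyses, and SAP 7.2 lets lesser changes be described in the study report. The optional single-subject plots let a reader set an event against that subject's earlier data.

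Most of this stands, and it limits the point to an improvement. It does not remove it: open-ended wording and optional plots do not commit the plan to a window or an interval, and the plots give no precision.

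Redaction is the second reply. Text is blacked out in protocol 14.2.2, SAP 7.9.3 and SAP 7.9.4; the feature table is blacked out as well, and the figures are not shown. A reference period or error bars could sit there. The point is therefore conditional on those parts not already covering it.

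A reader might go further and infer that the plan cannot assess change, that it reports no dispersion, or that it needs a significance test. The documents support none of these. The aligned daily means show the change, standard deviations are named, and a test is not required where no hypothesis is stated.

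**Conclusion.** The point holds as a cheap improvement, not as an error that harms the study. In the visible text, the mean pre-event change has no stated own-baseline window and no precision, and daily means and SDs cannot supply the precision.

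Under the assumed SD of 1 and the correlations in the table, the half-width is about 0.05 to 0.38 SD with 40 subjects and 0.08 to 0.56 SD with 20. The true values depend on correlations that the documents do not give, so the interval may prove tight or wide.

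The point does not apply to any feature already expressed relative to the subject's own reference, to laboratory values taken at scheduled visits, or to anything that the redacted text already settles.

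**What to change.** In SAP 7.9.4, keep the planned curve and show it from day -30; the 14 days are only a minimum. For each daily device feature not already expressed relative to the subject's own reference, add one pre-specified summary:

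- the mean within-subject change from an early window in the required 30 days (for example days -30 to -24) to one headline range (for example days -7 to -1), first event per subject;
- a paired 95% confidence interval, labelled descriptive and unadjusted for multiplicity;
- the number of subjects contributing.

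Daily intervals and further curves are optional. With 14 unadjusted daily intervals per feature, the chance that at least one excludes zero when nothing changes could reach 1 - 0.95^14 = 51% if they were independent. That favours a single headline range.

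The cost is a few sentences of SAP wording and a few lines of code, with no new data. There are three downsides. Drift that begins at day -21 or day -30 would show as about 85% or 79% of the day -1 change. The shorter baseline is slightly less precise. Unadjusted intervals across many features may still be over-read.

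### The SAP averages device data for 14 days after an event but requires data only before it, so the post-event mean can shift because its set of subjects changes (minor; cheap to improve)

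*Combined protocol and SAP*

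**What the plan says.** The entry rule looks backwards only. SAP 7.4 states that "an ADHF event must have LINQ™ data downloads for at least the most recent 30 days prior to the event". SAP 7.2 starts the analysis once at least 40 adjudicated events come from subjects who "have data for the most recent 30 days prior to the event". Protocol 14.4 is worded differently but points the same way: "an ADHF event must have complete LINQ™ data downloads prior to the event".

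The averaging in SAP 7.9.4 looks both ways. Each feature is reduced to one mean per subject per day. These are then averaged across subjects around the first event, including "each day following that event for a minimum of 14 days on either side of admission". The worked example begins "if 40 subjects have at least one ADHF event, then for each of the 14 days prior to that event", averages those 40 subjects' values, and ends with "The same will be done for the 14 days following ADHF admission".

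On gaps, SAP 7.4 says "Missing data will not be imputed" and closes with "If device data are missing, the event will not be included in the primary analysis". It does not say whether that last sentence extends to days after the event. SAP 7.9.4 also says that data captured before an early exit are used. The visible text specifies no fixed set of subjects, no within-subject change and no count of subjects per day.

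**The concern.** A mean over days is easy to read as the course of a typical subject. That reading is safe only if the same subjects are behind every point. Before the event they are, because the entry rule guarantees 30 days of data. After the event nothing guarantees it.

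The documents themselves provide routes by which data can stop:

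- SAP 7.1.1 lists death, exit and early closure as reasons for not completing follow-up.
- Protocol 8.15 requires exit after explant without a study replacement, and protocol 8.16 ends data collection at exit.
- SAP 7.8 allows all subjects to be exited once the required events have accrued, which could cut short the window of the latest ones.
- Protocol 8.12 relies on a monthly manual transmission, so a last download inside the window ends the record there.

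If those who drop out had worse values, the mean of the others moves towards normal. A feature could then seem to track decompensation and recovery when nobody recovered. SAP 7.9.3 says the data will feed later hypothesis generation, so such a pattern could influence which features are pursued.

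**Working it through.** The plan has no figure of its own for this quantity, so there is none to reproduce. The check asks how far the mean can move when no subject changes.

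**Inputs.** n = 40 subjects comes from the worked example in SAP 7.9.4. Two inputs are assumptions, because the documents give neither: k, the number whose data stop by day 14, and d, how much worse those subjects are than the rest, in between-subject SDs.

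**Formula.** Hold every subject's value flat after the event and let a higher value mean worse. The mean of all n is [(n − k) × stayers' mean + k × leavers' mean] / n. Subtracting this from the stayers' mean gives

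shift = (k/n) × (stayers' mean − leavers' mean) = −(k/n) × d,

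that is, an apparent improvement of (k/n) × d.

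**Results (SD units, n = 40).**

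| k lost | share | d = 1 | d = 1.5 | d = 2 |
|---|---|---|---|---|
| 1 | 2.5% | 0.025 | 0.0375 | 0.05 |
| 2 | 5% | 0.05 | 0.075 | 0.10 |
| 4 | 10% | 0.10 | 0.15 | 0.20 |
| 6 | 15% | 0.15 | 0.225 | 0.30 |
| 8 | 20% | 0.20 | 0.30 | 0.40 |

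**Yardsticks.** The standard error of a 40-subject mean is 1/√40 = 0.158 SD. The standard error of a mean paired change is √(2(1 − ρ)/40), where ρ is the assumed within-subject correlation: 0.10 SD at ρ = 0.8 and 0.158 SD at ρ = 0.5. For 1 to 4 subjects lost at d = 1, the shift is below 0.158 throughout and only reaches 0.10 at k = 4. It passes 0.158 with heavier or more selective loss, such as 8 lost at d = 1 (0.20) or 4 lost at d = 2 (0.20).

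**Sign.** The direction can even be wrong. If 4 of 40 leave who are 1 SD worse, and every remaining subject worsens by 0.05 SD, the mean changes by 0.05 − 0.10 = −0.05 SD, an apparent improvement.

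**Simulation.** In 4,000 runs per setting with n = 40, subjects were flat and the log hazard of leaving rose by 1 per SD of severity. Losses of about 2.4%, 4.7%, 8.8% and 16.2% gave apparent improvements of 0.024, 0.047, 0.087 and 0.155 SD. With loss independent of severity, the shift was at most 0.002 SD in size.

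**With a fixed set.** The mean within-subject change, taken over subjects with data on both sides, is exactly zero when nobody changes.

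**The case against.** *The SAP may already fix the set.* Read literally, doing the same after the event means averaging the same 40 subjects, and the closing sentence of SAP 7.4 could exclude any event without post-event data. SAP 7.9.5 refers back to 7.4. A reader might infer that the SAP plainly averages whoever has data each day, but it does not say so. What stands is that the text is open. If the exclusion does reach post-event days, the set is fixed but limited to subjects with post-event data, and that too needs stating.

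*The losses are narrower than they look.* With monthly transmission, having the 30 days up to the event usually requires a download on or after the event day. A subject who never transmits again will usually fail the entry rule and leave both means. This stands. What remains is mainly subjects with a last download inside the window, exit or explant inside it, or a device interrogation after death, which protocol 11.5.1 asks for when possible.

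*Those lost need not be sicker.* A reader might infer that the post-event set is healthier as a matter of fact. The documents do not show this. Protocol section 4 links HF hospitalization to mortality, which makes it plausible for deaths, but gives no rate for the days after an event. Closure at 40 events, missed transmissions and relocation need not follow severity.

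*The study is descriptive.* There is no hypothesis (SAP 7.9.1) and no performance requirement (SAP 7.9.2), and the objective concerns changes before events. This stands and limits the weight of the point. It does not remove it, because SAP 7.9.4 chooses to present post-event means and a reader without daily counts cannot tell whether a shift is trivial.

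**Conclusion.** The gap is real and minor. Entry depends on pre-event data, post-event days are averaged with no visible rule for missing ones, and such a mean can move without any within-subject change. Assuming 1 to 4 of 40 subjects lost and 1 SD worse, the movement is 0.025 to 0.10 SD towards apparent recovery, mostly below one standard error. It is zero if loss is unrelated to severity. Both the number lost and the severity gap are assumptions.

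A stronger reading would be that the study's main result is biased. The documents do not support it: with events admitted on pre-event data, later loss does not alter the pre-event curve. Nor do they support taking a shift of 0.2 SD or more as expected, since that needs loss or selectivity beyond the range above (for example 6 of 40 lost at 1.5 SD).

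**What to change.** In SAP 7.9.4:

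1. Keep the daily means over all available subjects and the full pre-event curve. Restricting the profile to subjects with data on both sides would condition the pre-event curve on later survival and data capture, and would conflict with the SAP's statement that all collected data enter the analysis. The paired summary should be added, not substituted.
2. Report the number of subjects contributing on each day.
3. Add the mean within-subject change from a stated pre-event reference period, in the fixed set of subjects with data on both sides of the event. Base any pre/post statement on this.
4. List deaths, exits and other loss of device data within 14 days after the event.
5. State whether the last sentence of SAP 7.4 applies to post-event days.

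The cost is a little more programming and no new data collection. The paired summary will have slightly fewer subjects and describes only those with post-event data, which its label should say.
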